8.9. Occupational Safety

No specific risks have been identified for staff handling SMT C1100. The Material Safety Data Sheet will be made available where required by local regulations.

9. CONCOMITANT MEDICATIONS AND NON-DRUG THERAPIES

9.1. Permitted Medications

Permitted medications include the following:

- Systemic corticosteroids (required for 6 months prior to study entry with stable dose [intermittent dosing is allowed] for at least 6 months prior to start of trial), including but not limited to, prednisolone, prednisone and deflazacort
- Angiotensin converting enzyme inhibitors (e.g., perindopril and lisinopril)
- Angiotensin-receptor blockers (e.g., losartan, irbestartan, valsartan and candesartan)
- Bisphosphonates (oral and intravenous), Vitamin D and calcium supplements

Investigators should use caution when concomitantly administering SMT C1100 and drugs that are substrates of OATP1B1 and/or OATP1B3 e.g., angiotensin-converting enzyme inhibitors, and angiotensin II receptor antagonists. They should monitor patients closely for signs and symptoms of excessive exposure to the drugs that are substrates of OATP1B1/1B3 and consider reduction of the dose of these drugs.

9.2. Prohibited Medications

Use of the following therapies is prohibited during the study and for at least five half-lives prior to the start of dose administration, unless otherwise stated below:

Study Number: SMT C11005	Compound No.: SMT C1100
Protocol	Version: 5.0 24Feb2017

- Substrates of CYP2B6 e.g., Ketamine, Pentobarbital, Lidocaine (see Appendix 1 for further details), except as used for anaesthesia during the study-required biopsy in a hospital setting.
- Inducers of CYP1A1 and/or CYP1A2 e.g., Omeprazole, Carbamazepine, Rifampin (see Appendix 1 for further details)
- Nicotine, including exposure to daily passive smoking (including parent/legal guardian, siblings) to minimise CYP1A induction
- Herbal supplements and homeopathic preparations should be stopped 7 days prior to the start of the Treatment Phase
- Substrates of BRCP (e.g., omeprazole, rabeprazole, fluvastatin, methotrexate, mitoxantrone, imatinib, irinotecan, lapatinib, rosuvastatin, sulfasalazine, topotecan)
- Beta-blockers (these may be started during the study if required but patients must not be enrolled whilst taking them)
- All prescription, OTC, and herbal products that are known CYP2B6 sensitive substrates (e.g., bupropion, efavirenz) will be excluded from 14 days prior to study conduct through to 14 days after study conduct completion. Please note, this is not an exhaustive list of CYP2B6 substrates and a discussion with the medical monitor may be warranted. Further details of CYP2B6 substrates are found in Appendix 1.
- Be using drugs that have serotonergic, norepinephrine or dopaminergic activity (e.g., selective serotonin reuptake inhibitors, serotonin norepinephrine reuptake inhibitors, tricyclic antidepressants, tryptophan, dextromethorphan, meperidine, bupropion, nortriptyline, desipramine, doxepin, amoxapine, rasagiline, selegiline), or treatments used in attention deficit hyperactivity disorder such as Methylphenidate, and phenethylamine (PEA).

In the interests of patient safety and acceptable standards of medical care the Investigator will be permitted to prescribe treatment(s) at his/her discretion. All treatments must be recorded in the patient's source documents and transcribed to the CRF (medication, dose, treatment duration and indication).

10. PATIENT COMPLETION AND WITHDRAWAL

10.1. Patient Completion

A patient will be classed as having completed the study at the end of the 30-day Safety Follow-Up unless they are rolled into the Extension Phase.

Study Number: SMT C11005 Protocol	Compound No.: SMT C1100 Version: 5.0 24Feb2017
---	---

10.2. Patient Withdrawal

10.2.1. Patient Withdrawal from Investigational Medicinal Product

A patient will be withdrawn from treatment for any of the following reasons:

- Withdrawal of consent/assent to continue taking treatment
- The study Investigator or Sponsor, for any reason, decides the patient should be withdrawn from the treatment
- Adverse events, classed as possibly or probably related by the Investigator, which cannot be tolerated by the patient

If a patient is withdrawn from treatment where possible they should continue to attend all remaining study visits so that data can be collected. If patients will not assent or their parents/guardian will not consent to this then they should be withdrawn from the study.

10.2.2. Patient Withdrawal from Study

A patient will be withdrawn from the study for any of the following reasons:

- Lost to follow-up
- Withdrawal of consent/assent
- Patient is not in compliance with requirements of the study
- Death
- The study Investigator or Sponsor, for any reason, decides the patient should be withdrawn from the study
- The study Investigator or Sponsor, for any reason, stops the study

If a patient is lost to follow-up, every possible effort must be made by the study centre personnel to contact the patient and determine the reason for discontinuation. The measures taken to follow-up must be documented.

When a patient withdraws before completing the study, the reason for withdrawal is to be documented in the source documents and transcribed to the CRF. Study drug assigned to the withdrawn patient may not be assigned to another patient.

Where possible any patient that withdraws from the study will complete the Early Termination Visit as outlined in the Time and Events Table.

Study Number: SMT C11005 Protocol	Compound No.: SMT C1100 Version: 5.0 24Feb2017
---	---

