Consequently it was hypothesised that SMT C1100 exposure could be improved by dietary manipulation. In study SMT C11003, patients with DMD were requested to take their doses with 100 mL full-fat milk and follow a balanced diet. The data from SMT C11003 supported the hypothesis demonstrating improved exposure of SMT C1100. As discussed above, these concentrations have been shown, *in vitro*, in both human myotubes and DMD myoblasts, to upregulate utrophin. Patients who were involved in both the SMT C11002 and SMT C11003 studies showed increased exposure when they took SMT C1100 with milk in the SMT C11003 study compared to the SMT C11002 study where milk was not required to be consumed with SMT C1100. Results in Study SMT C11004 showed that the F6 formulation of SMT C1100 had significantly improved pharmacokinetic properties with higher C_{max} and AUC's achieved (greater than six-fold increase in maximum SMT C1100 plasma levels), and was safe and well tolerated at doses up to the maximum dose used, 1 g *bid*. Consequently this formulation and dose will also be investigated in a small number of patients in Study SMT C11005.

By allowing all patients with DMD, irrespective of SMT C1100 levels, to participate in this study, we aim to address some of the questions about appropriate utrophin levels for benefit as even low plasma levels of SMT C1100 may modulate utrophin muscle levels enough to be of some clinical benefit.

With the low SMT C1100 exposure partly mitigated by asking patients with DMD to follow a balanced diet and consume 100 mL milk with SMT C1100 and with the development of formulation (F6), the next stage of SMT C1100 development is SMT C11005, a proof-of-concept study.

In two different studies (SMT C11002 and SMT C11003), each of which enrolled 12 patients, patients with DMD were exposed to SMT C1100 for between 11–14 days. Including SMT C11004 there is a total SMT C1100 exposure, in all previous studies, of 615 dosing days in 22 individual boys with DMD. In contrast, should all patients complete the SMT C11005 study per protocol the total SMT C1100 exposure in days will be considerably greater (15,120 dosing days) increasing even further if all elect to continue in the Extension Phase. By measuring pharmacokinetic endpoints of SMT C1100, and its DHD metabolites, at different time points throughout the study Summit will examine the correlation between systemic exposure and longer term safety.

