4.2.2. Individual Stopping Rules

The pharmacokinetics of SMT C1100 parent and metabolites, and their relationship with all safety parameters, will be reviewed on an ongoing basis by the Sponsor and the DMC. As this is an open-label study, the decision to stop individual patients may be made on a case-by-case basis. The DMC can also recommend, in individual patients, a lowering of the SMT C1100 dose.

If a patient's results meet either of the criteria below, dosing should be stopped and the tests should be repeated as soon as possible. If the repeated results still meet this criterion, the study drug will be permanently stopped and may not be restarted although the patient will continue to be followed for functional and MRI assessments for the duration of the study. If the patient is withdrawn from the study, a follow up visit should be arranged:

- GLDH \geq 3x ULN

Study Number: SMT C11005 Protocol	Compound No.: SMT C1100 Version: 5.0 24Feb2017
---	---

OR

- Bilirubin $\geq 2x$ ULN together with an INR $\geq 1.5x$ ULN (Cohort 2 and 3 only)

Any intolerable AE or SAE that is at least possibly related to study drug should lead to a temporary discontinuation of the patient's study treatment. After resolution of the intolerable AE or SAE, the Investigator, in discussion with the Sponsor, may decide to either permanently discontinue the patient's study treatment, or, if recommended by the DMC and Sponsor reinstate treatment but reduce their *bid* dose to 1.25 g for Cohort 1 and 3 or reduce the frequency to once-daily dosing (2.5 g or 1.25 g for Cohorts 1 and 3; 1 g for Cohort 2; see Section 8.1.1). If a lowered dose is tolerated for at least 2 weeks the Investigator can, based on the recommendation of the DMC and Sponsor escalate the dose up to the original strength. Once-daily dosing should occur in the morning.

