5. STUDY POPULATION

5.1. Number of Patients

A suitable number of potential patients will be screened in order that approximately 55 patients successfully meet the inclusion and exclusion criteria and continue into the Treatment Phase. Approximately thirty patients are expected to be enrolled in Cohort 1, approximately 10 in Cohort 2 and approximately 15 in Cohort 3. The sample size is not based upon statistical powering, but the number is considered as sufficient to initially explore the endpoints and their relationship with SMT C1100 plasma exposure.

Patients who withdraw or who are withdrawn during the Treatment Phase may be replaced if the study has not yet reached full enrolment at the time of withdrawal. Patients who withdraw or who are withdrawn for an AE considered related to SMT C1100 will not be replaced.

Efforts will be made, in Cohorts 1 and 2, to balance the study populations and attempt to have at least 50% of the boys with a fat:water fraction greater than or equal to 0.15. Efforts will also be made such that half of the boys are greater than or equal to 8 years of age at screening. Such attempts will be made manually rather than via an automatic system; achieving these recruitment goals will be attempted but complete balance will not be enforced.

All patients in Cohorts 1–3, will be eligible to be rolled into the Extension Phase.

Study Number: SMT C11005 Protocol	Compound No.: SMT C1100 Version: 5.0 24Feb2017
---	---

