8.7. Product Accountability and Assessment of Compliance

In accordance with GCP, each study centre will account for all supplies of SMT C1100 provided to them. Details of receipt, storage, assembly and return will be recorded. The unit of accountability will be one bottle of SMT C1100.

All unused supplies of SMT C1100 will either be destroyed or returned to the study Sponsor at the end of the study in accordance with instruction by the Sponsor.

Patients will be counted as compliant with the protocol if they take ≥95% of their medication as scheduled.

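### Protocol 10.2.2 makes undefined non-compliance a mandatory exit from the study, although boys who stop drug altogether stay in follow-up; later leg MRI and functional data can be lost needlessly

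*Protocol*

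**What the plan says.** Protocol 10.2.2 opens its list with "A patient will be withdrawn from the study for any of the following reasons". One entry, alongside death and loss to follow-up, is "Patient is not in compliance with requirements of the study". The section does not say which requirements count, how far a boy must fall short, or whether he could stay under observation. It asks for an Early Termination visit where one is possible.

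Other sections take a different approach to boys who are off drug:

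- Protocol 10.2.1, on withdrawal from treatment: "where possible they should continue to attend all remaining study visits so that data can be collected". A boy leaves the study only if assent or consent for this is refused.
- Protocol 4.2.2, after a confirmed liver stopping criterion: "the patient will continue to be followed for functional and MRI assessments for the duration of the study".
- SAP 5.1 includes data in the analyses whatever the interval since the last dose, with optional extra summaries that leave out late off-drug assessments.

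There are two definitions of medication compliance. Protocol 8.7: "Patients will be counted as compliant with the protocol if they take ≥95% of their medication as scheduled". SAP 9.4.1 puts the cut-off at 80% and tabulates three bands (below 80%, 80% to below 95%, 95% and above). Section 10.2.2 refers to neither.

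On replacement, protocol 5.1 says: "Patients who withdraw or who are withdrawn during the Treatment Phase may be replaced if the study has not yet reached full enrolment". Boys who leave because of a drug-related adverse event are excepted.

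**The concern.** As written, a boy who takes no drug at all after Week 10 is scanned and tested to Week 48 where possible, while a boy judged non-compliant in some unspecified way must leave. The protocol gives no reason for treating the second boy more strictly, and his data are of a kind the SAP is prepared to analyse.

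Change in leg MRI, and its relation to plasma concentration, are primary objectives in Cohorts 1 and 2. The rationale wants a broad exposure range: "By allowing all patients with DMD, irrespective of SMT C1100 levels, to participate in this study". Missed doses, or lapses in the fed-state and milk instructions, could plausibly both trigger the rule and lower exposure, so the loss may be informative. With no concurrent control, a shift caused by selective loss at later visits could not be told apart from a drug effect.

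**Working it through.** The documents give no power, drop-out or adherence figure (protocol 5.1 says the sample size is not powered), so there is no planned number to reproduce. The checks below cover the text, the trigger and the possible size.

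**1. What is lost and what is kept**

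- Kept: every dosed boy is in the ITT set (SAP 6.2), and one assessment, even baseline, puts him in an endpoint population (SAP 6.4). All data before withdrawal stay. The Early Termination visit includes functional tests, plus leg MRI if none was done in the previous 6 weeks (SAP 5.3.1), and can fill an analysis window (SAP 5.1).
- Lost: every later scheduled visit. Missed visits are not imputed (SAP 9.1.1), and leg MRI/MRS is never imputed (SAP 5.3.1).
- Example: a boy is scanned at Week 12 (Day 84) and withdrawn at Week 13 (Day 91). The last scan is 7 days old, so no Early Termination scan is due. He keeps one of four post-baseline leg scans and loses Weeks 24, 36 and 48. He can have the Week 12 trough used in SAP 9.10.1, but no later response to set against it.

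**2. Width of the ambiguous zone, if medication compliance is the trigger**

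Scheduled doses: 48 weeks × 7 days × 2 = 672.

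| Cut-off | Doses needed | Most that can be missed | One more missed |
|---|---|---|---|
| 95% (protocol 8.7) | 0.95 × 672 = 638.4 | 33 (639/672 = 95.1%) | 34 (638/672 = 94.9%) |
| 80% (SAP 9.4.1) | 0.80 × 672 = 537.6 | 134 (538/672 = 80.1%) | 135 (537/672 = 79.9%) |

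A boy missing 34 to 134 doses is non-compliant under one and compliant under the other. One missed dose a week (13/14 = 92.9%) falls in this zone. The SAP's main measure counts days, not doses; on 336 days the most that can be missed is 16 days at 95% and 67 at 80%.

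**3. Possible shift in a later-visit mean (assumed inputs)**

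Let k of the 40 boys in Cohorts 1 and 2 be withdrawn, with mean change g SD worse than the boys who stay. The mean among those who stay exceeds the mean for all 40 by (k/40) × g.

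| k | g = 0.25 | g = 0.5 | g = 1.0 |
|---|---|---|---|
| 2 | 0.013 | 0.025 | 0.05 |
| 4 | 0.025 | 0.05 | 0.10 |
| 8 | 0.05 | 0.10 | 0.20 |

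**4. Possible effect on an exposure-response correlation (assumed inputs)**

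This was simulated with 10,000 runs, bivariate normal data and n = 40, removing the k boys with the lowest exposure. That is the extreme case, because adherence is only one cause of low exposure.

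| Average correlation, all 40 | 4 removed | 8 removed |
|---|---|---|
| about 0.30 | 0.26 | 0.23 |
| about 0.49 | 0.44 | 0.40 |

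The correlation is weakened. This does not create a spurious relation.

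**The case against.** The strongest reply is that the entry is standard wording which the rest of the plan does not treat as an automatic exit. SAP 9.2 counts missed visits at each scheduled visit, SAP 9.3 reviews and tabulates important deviations, and SAP 9.4.1 has a band for boys below 80%. All three expect imperfectly compliant boys to remain. This stands as evidence of intent, but a site follows the protocol, and 10.2.2 tells it to withdraw the boy.

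Three stronger readings are tempting and are not supported:

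- A reader might infer that missing one dose a week forces withdrawal. Section 8.7 only classifies boys as compliant or not, 10.2.2 does not cite it, and at the SAP cut-off that boy is compliant.
- A reader might infer that low-exposure or weak boys are removed from the endpoints. They stay in the analysis sets with their data to withdrawal. No section calls a low plasma level non-compliance, and the protocol links low exposure largely to diet and formulation. SAP 5.2 treats physical inability as informative missing data.
- A reader might infer that such boys are swapped for better ones. Replacement is optional, ends at full enrolment, and adds a boy without deleting the first boy's data.

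Two further points stand. Retention under 10.2.1 is itself only where possible and depends on consent or assent. And the investigator or sponsor may still withdraw a boy for any reason, so deleting one entry does not guarantee follow-up. It does end an exit that the text makes compulsory.

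**Conclusion.** The point holds as an avoidable weakness in data collection. A mandatory and undefined rule conflicts in approach with 10.2.1, 4.2.2 and SAP 5.1, and following it costs later, non-imputed leg MRI and functional data in a study with no control arm. The conflict between the 95% and 80% definitions is a matter of text and needs no assumption.

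The size is unknown. No document gives an adherence rate or says how often the rule would be used. The range of 0.01 to 0.20 SD rests on 2 to 8 of 40 boys leaving with a mean change 0.25 to 1.0 SD worse; if those who leave do not differ, there is no shift in the mean, only fewer data. This is modest for an exploratory study and does not invalidate it, but it is worth an amendment because the loss is so easily prevented.

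**What to change.** 1. In protocol 10.2.2, remove non-compliance from the mandatory reasons for study withdrawal.
2. Add that non-compliance with drug or procedures is recorded as a protocol deviation, and that the boy continues his scheduled leg MRI, functional and safety visits as in 10.2.1 unless consent or assent is withdrawn.
3. In protocol 5.1, state that a boy kept in follow-up is not replaced.
4. Reconcile the compliance definitions in protocol 8.7 and SAP 9.4.1, including whether doses or days are counted.

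Decisions about study drug are left as they are. The cost is a short protocol amendment and a matching SAP edit. The downside is a few visits for poorly adherent boys, all already in the 48-week schedule.

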10.3. Treatment after the End of the Study

No IMP will be provided after the end of the Treatment Phase unless the subject continues into the Extension Phase.

10.4. Screen and Baseline Failures

Data collected from screening failures will be limited to reason for screen failure and related data.

11. ADVERSE EVENTS AND SERIOUS ADVERSE EVENTS

11.1. Adverse Events

An AE is any untoward medical occurrence in a patient or clinical investigation patient administered a pharmaceutical product and which does not necessarily have a causal relationship with this treatment. An AE can therefore be any unfavourable and unintended sign (including an abnormal laboratory finding), symptom, or disease temporally associated with the use of a medicinal (investigational) product, whether or not related to the medicinal (investigational) product.

Adverse events will be recorded from the signing of the consent form until the end of the safety follow-up period or completion of the Extension Phase.

11.1.1. Causal Relationship

Causal relationship assessment to drug treatments is required for purposes of reporting AEs. To promote consistency, the following guidelines should be taken into consideration along with good clinical and scientific judgment when determining the relationship of drug treatments to an AE:

- Probable relationship: event occurs in a plausible time relationship to the medication administration and cannot be explained by concurrent disease or other drugs or chemicals; the response to the withdrawal of the drug should be clinically plausible
- Possible relationship: event occurs with a reasonable time sequence to the medication administration, but could also be explained by concurrent disease or other drugs or chemicals; information on the drug withdrawal may be lacking or unclear
- Unlikely relationship: event occurs with little temporal relationship to the medication administration and other factors such as drugs, chemicals or underlying disease provide plausible explanations

Study Number: SMT C11005	Compound No.: SMT C1100
Protocol	Version: 5.0 24Feb2017

- Not related: event has no temporal relationship to the medication administration or there is a definite alternative aetiology

11.1.2. Severity Criteria

An assessment of severity grade will be made using the following general categorical descriptors:

- **Mild:** awareness of symptoms that are easily tolerated causing minimal discomfort and not interfering with everyday activities
- **Moderate:** sufficient discomfort is present to cause interference with normal activity
- **Severe:** extreme distress causing significant impairment of functioning or incapacitation. Prevents normal, everyday activities

The Investigator should use clinical judgment in assessing the severity of events not directly experienced by the patient (e.g., laboratory abnormalities).

11.1.3. Reporting Adverse Events

All AEs and special reporting situations, whether serious or non-serious, will be reported from the time a signed and dated informed consent form is obtained until completion of the patient's last study-related procedure (which may include contact for follow-up of safety). The Sponsor will evaluate any safety information that is spontaneously reported by an Investigator beyond the time frame specified in the protocol.

All AEs, regardless of seriousness, severity, or presumed relationship to study therapy, must be recorded using medical terminology in the source document and the CRF. Whenever possible, diagnoses should be given when signs and symptoms are due to a common aetiology (e.g., cough, runny nose, sneezing, sore throat, and head congestion should be reported as "upper respiratory infection"). Investigators must record in the source documents and the CRF their opinion concerning the relationship of the AE to study therapy. All measures required for AE management must be recorded in the source document and reported according to Sponsor instructions.

The patient's parents or responsible adult must be provided, on Day 1, with a "study card" indicating the following:

- Patient's name
- Patient number
- Patient's date of birth
- Name of the investigational product

Study Number: SMT C11005 Protocol	Compound No.: SMT C1100 Version: 5.0 24Feb2017
---	---

- Investigator's name and 24 hour contact information
- Statement that the patient is participating in a clinical trial

